## **8.0 Data Collection and Management Procedures**

Each subject will be assigned a unique study ID. Study data will be collected following each clinic visit and recorded on the applicable case report forms (CRFs). Data will be coded to the subject study ID. The Enrollment Log, needed to link a subjects study code to identifiers, will be stored separately. Hard copies of CRFs and the Enrollment Log will be stored in locking file cabinets within the UIC College of Dentistry Clinical Research Center. Electronic documents will be stored on a secure departmental server. Only authorized UIC research personnel will have access.

## **9.0 Data Analysis**

Data analysis will be performed by the UIC PI in collaboration with the Co-I's using SPSS, SAS or similar software. A biostatistician may be consulted for statistical analysis, if required. Data will be de-identified prior to release to any statistician not listed as study personnel on Appendix P.

## **10.0 Quality Control and Quality Assurance**

The UIC investigators are clinicians who are trained to perform dental implant therapy (both with and without allografts) at the UIC College of Dentistry. Only trained UIC personnel will participate in the clinical care of UIC subjects.

Study data, including photographic records, hard copy CRFs and the electronic patient records of treatment, will be reviewed periodically by the PI and Coordinator. All investigators will be calibrated to the study protocol in an initiation meeting(s) before undertaking study intervention (visit #2; implant surgery). Outcomes regarding quality of care and records will be reviewed in monthly research team meetings.

## **11.0 Data and Safety Monitoring Plan**

### **11.1 Data Monitoring**

UIC data will be checked for errors and omissions by the UIC PI and authorized UIC research personnel and corrected on the CRFs in a timely fashion by authorized UIC research personnel.

### **11.2 Safety Monitoring Plan**

This protocol will be presented to the UIC Institutional Review Board for review and approval before the study commences. The IRB will be responsible for human subject protection oversight through annual periodic review of the research. All personnel participating in research activities at UIC will meet UIC IRB requirements for human subjects research, including completion of an approved CITI human subjects training and refresher courses at required intervals.

Each year, the UIC PI will submit a continuing review to the UIC IRB, which will review progress and re-approve the protocol. As part of these reviews, the UIC PI will report how many subjects have been recruited and if there have or have not been any adverse reactions reported by study participants.

The UIC PI or authorized UIC research personnel will obtain informed consent and will follow all protocols to assure compliance with standards of subject privacy. Data may be collected from the UIC subjects electronic dental record (AxiUm) and recorded on the appropriate Case Report Forms (CRFs) by the UIC PI, Co-I or authorized member of the UIC research team. Study data will be coded to a subjects ID and securely stored within the College of Dentistry Clinical Research Center. Data collection timepoints are: Screen/Enrollment, Implant, 1 week

follow up, 8 week follow up (Final Crown) and 12 month Follow-up. Access to UIC study data will be limited to the UIC PI, Co-Is and authorized members of the research team.

The UIC PI, assisted by the Co-Is, will monitor for adverse events occurring to UIC subjects.

An adverse event (AE) is defined as any untoward and unintended medical occurrence in a subject. A serious adverse event is defined as an unintended medical occurrence in a subject that: results in death, is life-threatening, results in hospitalization or prolongation of an existing hospitalization, results in persistent or significant disability/incapacity or a congenital anomaly/birth defect.

There are a number of expected adverse events related to implant with crown surgery, including bleeding and bruising after surgery, post-surgical pain, infection, delayed healing, temporary speech problems, bone fracture, temporary or permanent damage to the nerves of the jaw, loss of bone on the upper or lower jaw (including altered appearance of the gum line), infection in the bone, damage to the adjacent teeth, chronic pain, abscess, and infection of the gums which may be unrelated to the study intervention (allograft).

A risk of implant treatment is failure of the implant prior to restoration or 'early' failure due to the lack of Osseointegration. This is associated with no pain or infection and the implant can be easily removed. Following 8 weeks of healing of the site, an implant can be replaced. In this study, if an implant is lost in the patient receiving the gum graft, the gum graft would not be removed.

Adverse events related to the PerioDerm® allograft include local or systemic infection, dehiscence (*wound rupture along incision line*) and/or necrosis (*death of tissue*) due to poor revascularization and allergic response to component(s) of the graft.

The UIC subject's treating clinician, who may or may not be a member of the research team, will attend to these adverse events until they have resolved and/or will refer the UIC subject to the appropriate provider as needed. These anticipated adverse events are described in the informed consent document and will be recorded on the appropriate CRF. Implant failure will result in dismissal of the subject and appropriate referral to the local dentist or UIC College of Dentistry clinics for further treatment.

Serious adverse events that are both unexpected and considered to be related to the study intervention will be reported to the UIC IRB in accordance with UICOPRS reporting guidelines. Anticipated adverse events that are not serious but occur at a frequency or intensity greater than anticipated by current clinical practice knowledge will also be reported to the UICIRB in accordance with UICOPRS reporting guidelines.

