## **7.0 Expected Risks/Benefits**

The risks of dental implant therapy are minimal but include complications such as bleeding and bruising after surgery, post-surgical pain, infection, delayed healing, temporary speech problems, bone fracture, temporary or permanent damage to the nerves of the jaw, loss of bone on the upper or lower jaw (including altered appearance of the gum line), infection in the bone, damage to the adjacent teeth, chronic pain, abscess, and infection of the gums.

Risks of a PerioDerm® allograft include local or systemic infection, dehiscence (*wound rupture along the line of incision*) and/or necrosis (*death of tissue*) due to poor revascularization or allergic response to some component(s) of the graft material.

In accordance with the graft manufacturer's instructions, tissue recipient records for subjects receiving PerioDerm® will be maintained for the purpose of post-transplant tracing. This may increase the risk to the privacy of subjects randomized to +Graft.

CBCT and other 3D intraoral scanner capture light-generated images which are compiled by the appropriate software into a 3 dimensional geometric image. Since these scanners does not utilize xray technology, the medical risks of use are minimal and include mild fatigue of the facial muscles.

Subjects will be encouraged to contact the PI in the event of medical emergencies related to his/her dental care and will be provided a 24-hour emergency contact number. Subjects experiencing complication may require additional (>5) clinic visits during the course of this study. This is clearly indicated within the consent document.

If implant integration fails or the implant site is infected, the implant will be removed or the site infection treated using standard dental therapies. The subject will be excluded from this study and referred to UIC College of Dentistry for care.

Restoration of the oral cavity is likely to benefit all subjects, irrespective of study group. The potential for an enhanced restoration in the +Graft study group, as compared to the -Graft group, is the focus of this study.

Results from this research may lead to modifications in standards of care which may benefit future patients receiving dental implant therapy.

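### Rules for failed integration and site infection conflict between sections, and sections 7.0 and 11.2 end scheduled safety observation, after implant loss with the graft still in place

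*Combined protocol and SAP*

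**What the plan says.** Three parts of the protocol say what happens after these events.

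- **Section 7.0** names two triggers: "If implant integration fails or the implant site is infected, the implant will be removed or the site infection treated using standard dental therapies". It continues: "The subject will be excluded from this study and referred to UIC College of Dentistry for care".
- **Section 11.2** names implant failure only: "Implant failure will result in dismissal of the subject and appropriate referral to the local dentist or UIC College of Dentistry clinics". It adds: "In this study, if an implant is lost in the patient receiving the gum graft, the gum graft would not be removed". What happens to the graft after a site infection is not stated. The same section lists local infection, dehiscence and necrosis as adverse events of the graft.
- **Section 6.0**, fourth and fifth visits, has a failed implant removed and the patient referred, but leaves discontinuation from the study optional. The third to sixth visits each say that any complication seen will be managed by usual care. None mentions exclusion for infection.

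The plan has other safety provisions. Under section 11.2 the investigators have a general duty to monitor adverse events. Anticipated events are recorded on a case report form, and the treating clinician attends to them until resolution and/or refers the subject. Data may also be taken from the dental record (AxiUm). Under section 7.0 subjects "will be provided a 24-hour emergency contact number", and "Subjects experiencing complication may require additional (>5) clinic visits during the course of this study".

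**The concern.** The point concerns the safety record, not the efficacy analysis set.

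First, two investigators could treat identical patients differently and both be following the protocol. One would dismiss a subject with failed integration at week 8, and the other would keep the subject to one year. The same is true of a site infection, depending on whether section 6.0 or section 7.0 is read.

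Secondly, the mandatory version ends scheduled observation because of something that happened after randomisation. One trigger, local infection, is itself a listed harm of the randomised intervention. After the other, implant loss, the graft remains in the patient. A later dehiscence, necrosis or infection then reaches the study only through unscheduled routes. Section 11.2 has anticipated events reported to the IRB when they occur more often or more intensely than expected, and that judgement is only as good as the record behind it.

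**Working it through.** The plan states no figure on this point. The check is a comparison of the text, followed by a count of visits.

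**1. The rules side by side**

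| Place | Failed integration or implant failure | Site infection |
|---|---|---|
| 6.0, third visit (1 week) | Not named | Any complication: usual care, no exclusion |
| 6.0, fourth visit (8 weeks) | Removal and referral; discontinuation optional | Any complication: usual care, no exclusion |
| 6.0, fifth visit (10-12 weeks) | Removal and referral; discontinuation optional | Any complication: usual care, no exclusion |
| 6.0, sixth visit (1 year) | Not named | Any complication: usual care and referral |
| 7.0 | Exclusion mandatory | Exclusion mandatory |
| 11.2 | Dismissal mandatory | Listed adverse event, attended to and recorded; no dismissal |

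For failed integration, optional and mandatory rules cover the same event. For infection, the link is section 7.0, which lists infection among the complications of implant therapy. The complication sentence in each visit therefore covers it. Section 7.0 also allows for extra visits during the study in subjects with complications, which does not fit exclusion on infection. The rules conflict for both triggers.

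**2. Scheduled visits lost**

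Section 6.0 gives four post-surgical visits: 1 week, 8 weeks, 10-12 weeks and 1 year. Visits lost = 4 minus the visits completed up to and including the one at which the subject leaves.

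- Infection exclusion at week 1, if section 7.0 is applied: 4 - 1 = 3 of 4
- Dismissal at week 8: 4 - 2 = 2 of 4
- Dismissal at weeks 10-12: 4 - 3 = 1 of 4

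The data-collection timepoints in section 11.2 omit the 10-12 week visit. On that list the loss is 3 - 1 = 2 of 3 at week 1 and 3 - 2 = 1 of 3 at week 8.

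**3. How many subjects**

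The documents give no failure or infection rate. The target is 40 subjects, 20 per group (sections 5.0 and 12.0). The rates below are assumptions, used only to size the workload of the fix.

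| Assumed share meeting a trigger | Of 40 subjects | Of 20 graft recipients |
|---|---|---|
| 2% | 40 x 0.02 = 0.8 | 20 x 0.02 = 0.4 |
| 5% | 40 x 0.05 = 2 | 20 x 0.05 = 1 |
| 10% | 40 x 0.10 = 4 | 20 x 0.10 = 2 |

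These are expected numbers of subjects leaving observation, not of missed events. Missed events would also need the rate of later graft events in these subjects and the share that goes unreported. The documents give neither, so no estimate is made.

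**The case against.** The strongest reply is that safety cover does not stop at dismissal. The investigators' duty to monitor adverse events is general and not tied to visits, known events are attended to until resolved or referred, and subjects have an emergency number. That stands, and it rules out the reading that dismissed subjects have no safety cover. But none of it is a scheduled contact. The treating clinician is someone "who may or may not be a member of the research team", a subject with a failed implant may be referred to a local dentist, and use of the dental record is optional. Later events can be captured, but nothing ensures that they are.

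Four stronger readings are tempting, and the documents do not support them.

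- *Dismissed graft recipients are at raised risk.* Section 2.0 reports no increase in implant failure or complications with this type of graft. Section 11.2 says of early failure: "This is associated with no pain or infection and the implant can be easily removed". That describes the failure rather than the retained graft afterwards, but nothing in the text shows higher graft risk in these subjects.
- *Most of a year of observation is lost.* Retained subjects also have no scheduled visit between weeks 10-12 and 1 year. The fair measure is visits lost, not weeks.
- *A planned safety comparison is biased.* Adverse events are not an outcome in section 6.0, and no test between arms is planned. The yearly IRB report says whether adverse reactions have been reported, and it is not described as a count. The frequency check in section 11.2 is against clinical experience, not the other arm.
- *Section 11.2 also dismisses subjects for infection.* Its dismissal sentence covers implant failure only. The infection exclusion rests on section 7.0 alone.

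**Conclusion.** The point holds as an inconsistency for both triggers, and as a stated rule that, if followed, ends scheduled safety observation after implant failure (sections 7.0 and 11.2) or site infection (section 7.0 alone). The firm size is 2 of 4 post-surgical visits lost at week 8 and 1 of 4 at weeks 10-12. The figure of 3 of 4 at week 1 depends on applying section 7.0 to an infection where the visit description directs only usual care.

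A reader might go on to infer a probability of missed graft harm. That would need assumed rates of dismissal, of later graft events and of non-reporting, none of which the documents supply. The number missed cannot be estimated and is probably small. The failure itself can still be counted towards implant survival. The change is worth making because the wording needs reconciling at any event rate and the added follow-up is cheap.

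**What to change.** Align section 6.0 (third to sixth visits), section 7.0 and section 11.2 to one rule, for example:

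*Failed integration ends study implant treatment. Implant-site infection is treated by standard dental therapy. Neither event ends safety observation. With consent, adverse events are collected in both arms to 12 months from the randomised surgery by one telephone contact, with AxiUm review where the subject is treated at UIC. The date of any replacement implant or re-operation is recorded. These subjects are included in the adverse-event listing for all randomised and treated subjects.*

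**Cost.** Wording in three sections, a change to the consent form (whose current text could not be checked here), and one call per affected subject, with a record review for those treated at UIC. At the assumed 2% to 10% that is 0.8 to 4 of 40 subjects. No new clinic visit is needed.

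**Downside.** One call detects dehiscence or necrosis less well than an examination. Data for subjects treated elsewhere are self-reported. After a second surgery, attribution to the graft is uncertain, which is why the re-operation date is recorded.

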## **13.0 Regulatory Requirements**

**13.1 Informed consent.** UIC subjects participating in this study will provide informed consent and HIPAA authorization for the use of his/her personal health information in this research.

**13.2 Subject Confidentiality.** The privacy of the UIC study participants will be safeguarded by assigning each subjects a unique study code. Study data will be labeled with this code. An enrollment log, needed to link UIC subject identifiers to this study code, is stored separately. Only the UIC PI and authorized UIC study personnel will have access.

**13.3 Unanticipated Problems.** Unanticipated problems at UIC will be reported to the UIC IRB in accordance with UIC OPRS guidelines and as described above in section 11.2 Safety monitoring.

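### Unless 'unexpected' includes unexpected severity, a serious graft-related event of a listed type meets neither of section 11.2's event-driven IRB reporting rules

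*Combined protocol and SAP*

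**What the plan says.** Section 11.2 (Safety Monitoring Plan) sets two event-driven routes to the IRB.

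- Rule 1: "Serious adverse events that are both unexpected and considered to be related to the study intervention will be reported to the UIC IRB", following the institution's OPRS guidelines.
- Rule 2: "Anticipated adverse events that are not serious but occur at a frequency or intensity greater than anticipated by current clinical practice knowledge" are also reported, under the same guidelines.

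The section also sorts the events. "Adverse events related to the PerioDerm® allograft include local or systemic infection, dehiscence" and necrosis, and the list ends with "allergic response to component(s) of the graft". After this list and the list of implant-surgery events, the plan says: "These anticipated adverse events are described in the informed consent document and will be recorded on the appropriate CRF". Seriousness is defined by outcome. Besides death, disability and congenital anomaly, it covers an event that "is life-threatening, results in hospitalization or prolongation of an existing hospitalization".

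Two other IRB routes are stated. At the yearly continuing review, the principal investigator reports recruitment numbers and "if there have or have not been any adverse reactions reported by study participants". Section 13.3, under Regulatory Requirements, says: "Unanticipated problems at UIC will be reported to the UIC IRB in accordance with UIC OPRS guidelines and as described above in section 11.2".

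**The concern.** The two rules look as if they were meant to complement each other: one for serious surprises, the other for an excess of known milder problems. They do not meet. Rule 1 is limited by expectedness and rule 2 by non-seriousness, so an event that is both serious and of an anticipated type can fall between them.

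The result runs the wrong way for patient safety. If minor dehiscences occur more often than expected, the IRB must be told. If infections requiring hospitalization occur more often than expected, neither rule, read by event type, requires a report.

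At stake is when the IRB hears of such an event. The study team would know of it: section 11.2 has the principal investigator and co-investigators monitor adverse events, and section 10.0 provides monthly team meetings on quality of care. The IRB is the only oversight body outside the team that the documents name. Section 2.0 reports no increase in complications with a submucosal allograft, but it also says that the systematic review it cites included no allogeneic materials. That is a reason to keep the reporting of serious graft events unambiguous.

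**Working it through.** The plan gives no figure on this point, so the check is one of logic. The conditions in the text are:

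- Rule 1 applies if the event is serious, unexpected and related to the intervention.
- Rule 2 applies if the event is anticipated, not serious, and above the anticipated frequency or intensity.
- Infection, dehiscence, necrosis and allergic response are listed as related to the graft and called anticipated.
- Seriousness depends on outcome, so an event of a listed type can be serious.

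Applied to graft-related events, with expectedness judged by whether the type is listed:

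| Graft-related event | Rule 1 | Rule 2 |
|---|---|---|
| Serious, type not listed | applies | no (not anticipated) |
| Not serious, listed type, in excess | no (not serious) | applies |
| Serious, listed type, not in excess | no (anticipated) | no (serious, and no excess) |
| Serious, listed type, in excess | no (anticipated) | no (serious) |

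The last row is the anomaly. Frequency or intensity beyond expectation triggers a report in the second row but not in the fourth, where the harm is greater.

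The other routes, for the last two rows:

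1. Section 13.3 concerns unanticipated problems. An event that section 11.2 calls anticipated is not covered on its face, and the section refers back to 11.2.
2. The OPRS guidelines are not reproduced, so what they add cannot be checked.
3. The annual review clearly applies. Its stated content is whether adverse reactions have been reported, with no stated breakdown by seriousness, relatedness or arm.

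The check then turns on one word. Unexpected is not defined. If it includes unexpected severity, a hospitalized infection could be unexpected although infection is listed, and the last two rows could then fall under rule 1. The text points both ways. Rule 2 speaks of anticipated events whose intensity exceeds what was anticipated, so in the plan's vocabulary an event can be worse than expected and still be called anticipated. That favors reading by type. On the other hand, rule 2 also shows that the authors treated intensity as part of what is anticipated, and the lists name event types without saying that their serious forms are anticipated. That favors reading by severity.

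**The case against.** The strongest case against is that the authors cannot have meant the odd result. Rule 2 reads as an extension of reporting down to milder events, which presupposes that the worse ones are already covered by rule 1. Section 2.0 says that the cited soft-tissue grafting studies showed no untoward morbidity, so a life-threatening allergic response would plausibly count as unexpected whether or not allergy is listed. Limiting single-event reports to unexpected related events is also a defensible choice. Section 13.3 is worded additively, naming the OPRS guidelines as well as section 11.2, and may cover part of the gap. The rules are minimums, and nothing stops the investigator from reporting sooner.

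Most of this stands. It shows that the gap may not exist in practice and that its consequence is limited. It does not explain why rule 2 excludes serious events. If rule 1 already covers every serious form, the exclusion is harmless but unneeded. If it does not, the exclusion creates the gap. The reporting of serious harm should not depend on which reading staff choose.

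A reader might infer more: that serious graft events would go unrecorded, or that the IRB would certainly not hear of them before the annual review. The documents do not support either. Anticipated events are recorded on the case report form and monitored by the investigators, and both the severity reading and the unseen guidelines could require an earlier report.

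**Conclusion.** The point holds in a limited form. If unexpected is read by event type, a serious graft-related event of a listed type meets neither event-driven rule, even at excess frequency or intensity, while a non-serious excess must be reported. The annual review is then the clearly applicable remaining route.

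This rests on two things the documents leave open: the meaning of unexpected, and the content of the OPRS guidelines.

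The size cannot be put in numbers. The documents give no rate for serious graft events, and what they report suggests that such events are rare. A reader might also infer that a quantifiable number of subjects would be grafted without IRB protection. That would need assumed event rates and an IRB that acts on a single case, and the documents supply neither. The point does not affect the trial's outcomes or its inference. It is a cheap improvement to a safety rule.

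**What to change.** Make two wording changes in section 11.2.

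1. In rule 2, delete the phrase that confines it to non-serious events and put *, serious or not, that* in its place. The rule then covers any anticipated event above the expected frequency or intensity.
2. In rule 1, add: *An event of a listed type that meets this section's definition of serious counts as unexpected for this purpose.* Equivalently, require a report of every related serious event whether or not its type is listed.

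Leave timing to the OPRS guidelines, as both rules already do.

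The first change alone removes the anomaly for an excess. The second also settles the single serious event.

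The cost is a few words, with no new visit, committee or tabulation. The downside is possibly one extra IRB report over the trial, or none, and a single case cannot show that the graft caused harm.
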